11.3	Statistical criteria of termination of trial	37
11.4	Planned Analyses.....	38
11.4.1	Datasets to be analysed, analysis populations.....	38
11.4.2	Primary Analysis	38
11.4.3	Secondary Analyses	38
11.4.4	Interim analyses	38
11.4.5	Safety analysis	38
11.4.6	Deviation(s) from the original statistical plan	38
11.5	Handling of missing data and drop-outs.....	38
12.	QUALITY ASSURANCE AND CONTROL.....	39
12.1	Data handling and record keeping / archiving.....	39
12.1.1	Case Report Forms.....	39
12.1.2	Specification of source documents	40
12.1.3	Record keeping / archiving	40
12.2	Data management.....	40
12.2.1	Data Management System	40
12.2.2	Data security, access and back-up	40
12.2.3	Analysis and archiving	41
12.2.4	Electronic and central data validation	41
12.3	Monitoring.....	41
12.4	Audits and Inspections	41
12.5	Confidentiality, Data Protection	41
12.6	Storage of biological material and related health data.....	41
13.	PUBLICATION AND DISSEMINATION POLICY.....	41
14.	FUNDING AND SUPPORT.....	42
14.1	Funding	42
14.2	Other Support.....	42
15.	INSURANCE.....	42
16.	REFERENCES.....	43
17.	APPENDICES.....	45

STUDY SYNOPSIS

(ClinO, Appendix 3, 1.1, 2.1, 3.1, 4.1; Appendix 5, 2b; AGEK Summary)

Sponsor	Sonova AG (contact person: [contact]), [name], [name]
Principle Investigator	[name] ([contact]), [name], [name]
Study Title:	Quality Control of CE-Labelled Phonak Hearing Systems
Study ID:	CH-PH-Marketing-Validation
Protocol Version and Date:	Version 1.3, 17.12.2019
Trial registration:	After approval by CEC in: 
 • clinicaltrials.gov • Swiss Federal Complementary Database
Study category and Rationale	MD risk class IIA: Phonak Hearing Systems (comprising hearing aids, acoustic couplings and fitting software), Wireless Accessories (receiver), Smartphone Applications MD risk class I: Wireless Accessories (transmitters). All investigational devices are CE-labelled and their application is done according to the specialised information.
Clinical Phase:	“Phase of final inspection” (directly prior to launch)
Background and Rationale:	Phonak Hearing Systems pass through different development and study stages. At an early stage, feasibility studies are conducted to investigate new algorithms, features and functions in an isolated manner. If the benefit is proven, their performance is then investigated regarding interdependency between all available algorithms, features and functions running in parallel in a hearing aid (pivotal/pre-validation studies) and, as a result, they get optimized. Afterwards, and prior to product launch, the Phonak Hearing Systems undergo a final quality control in terms of clinical trials in the way as planned for this study (“phase of final inspection”).
Primary Objective(s):	Zero-defect overall performance of the new Phonak Hearing Systems: 
 • Technical: Sound quality, system stability and no distortions/artefacts/interruptions/feedback/system noise or other malfunctions occur. • Audiological: In the lab (objective: Standardised speech intelligibility measures in quiet/noise, threshold measures, cognitive measures, simulations of various listening situations, interviews) and in the users’ everyday life (subjective: questionnaires). • Handling: Rate of applicability, size, robustness, look-and-feel.
Secondary Objective:	Product benchmark: Comparison of new Phonak Hearing Systems to previous outstanding Phonak models and to competitor devices according to primary objectives.
Outcome(s):	
 • Lab trials: Objective and subjective test results • Home trials: Subjective test results
Study design:	Active comparator study, controlled, single blinded, randomised, cross-over or parallel design.

Inclusion / Exclusion criteria:	
Participants fulfilling all of the following inclusion criteria are eligible for the study:
 
 • Adult hearing impaired persons (minimum age: 18 years) with and without (experience with) hearing aids • Good written and spoken (Swiss) German language skills • Healthy outer ear (without previous surgical procedures) • Ability to fill in a questionnaire (p/eCRF) conscientiously • Informed Consent as documented by signature 
The presence of any one of the following exclusion criteria will lead to exclusion of the participant:
 
 • Contraindications to the MD in this study, e.g. known hypersensitivity or allergy to the investigational product • Limited mobility and not in the position to attend weekly appointments • Limited ability to describe listening impressions/experiences and the use of the hearing aid • Inability to produce a reliable hearing test result • Massively limited dexterity • Known psychological problems • Central hearing disorders
Measurements and procedures:	
Pure tone audiogram, speech intelligibility in quiet and noise, threshold measurements, cognitive measurements, rating of sound simulation, questionnaires, interviews.

Study Product / Intervention:	
MD risk category I and IIA

Control Intervention (if applicable):	
MD risk category I and IIA

Number of Participants with Rationale:	
In total, a maximum of 210 subjects will participate per year. According to experience, 6 clinical trials (main studies) with a maximum of 30 subjects per study are conducted for a quality control of the Phonak Hearing Systems prior to product launch. Additionally, a pre-study with 5 Sonova internal (normal hearing and/or hearing impaired) persons may take place to proof the respective study concept in advance if necessary.

Study Duration:	
10 years (01.10.2015 – 31.10.2025)

Study Schedule:	
Month Year of First-Participant-In: October 2015 Month Year of Last-Participant-Out: October 2025

Investigator(s):	
[name], [name], [name], [name], [name] Sonova AG, [name], [contact]

Study Centre(s):	
Single-centre (Sonova AG, Stäfa)

Statistical Considerations:	
Sample size according to experience and to established specialized literature.
 
Descriptive statistics: Frequency distribution, mean and standard deviation, median and quartile, boxplot, histogram, scatterplot.
 
Inferential statistics: t-Test, Mann-Whitney-U-Test, Wilcoxon-Test, correlation coefficient (Pearson, Spearman) .

GCP Statement:	
This study will be conducted in compliance with the protocol, the current version of the Declaration of Helsinki, the ICH-GCP or ISO EN 14155 (as far as applicable) as well as all national legal and regulatory requirements.

STUDY SUMMARY IN LOCAL LANGUAGE

In dieser Studienreihe findet eine methodische klinische Evaluation von neuen CE-zertifizierter Phonak Hörsystemen zur Qualitätskontrolle vor dem jeweiligen Produktlaunch statt. Das Ziel der Untersuchungen ist es, mithilfe von hörgeschädigten Studienteilnehmern, eine fehlerfreie Leistungsfähigkeit des gesamten Phonak Hörsystems zu gewährleisten. Das Phonak Hörsystem umfasst Hörgeräte unterschiedlicher Formfaktoren, akustische Ankopplung, drahtloses Zubehör (z.B. Fernbedienung) sowie die Anpass-Software. Des Weiteren wird die Sicherstellung des maximalen Nutzens für den Träger des Hörsystems anhand von objektiven Labormessungen sowie von subjektiven Bewertungen beim Tragen im Alltag angestrebt. Im Zuge dieser Untersuchungen werden die neu entwickelten Phonak Produkte mit ihren Vorgängermodellen sowie mit Mitbewerberprodukten verglichen. Diese klinische einfachblinde Studienserie erfolgt unter kontrollierten, randomisierten Bedingungen am Hauptsitz der Sonova AG in Stäfa.

ABBREVIATIONS

Provide a list of abbreviations used on the protocol - to be completed

AE	Adverse Event
ANL	Acceptable Noise Level
BTE	Behind-The-Ear device
CA	Competent Authority (e.g. Swissmedic)
CEC	Competent Ethics Committee
CRF	Case Report Form
CU	Categorical Unit
ClinO	Ordinance on Clinical Trials in Human Research (in German: KlinV, in French: OClin)
CTCAE	Common terminology criteria for adverse events
dB	Decibel
DD	Device Deficiencies
DM	Digital Modulation
DSUR	Development safety update report
eCRF	Electronic Case Report Form
pCRF	Paper Case Report Form
FM	Frequency Modulation
GCP	Good Clinical Practice
GöSa	Göttinger Satztest
IB	Investigator's Brochure
ITE	In-The-Ear device
Ho	Null hypothesis
H1	Alternative hypothesis
HFG	Humanforschungsgesetz (Law on human research)
HIBAN	Hearing Instrument Body Area Network
HMG	Heilmittelgesetz
HRA	Federal Act on Research involving Human Beings
IMP	Investigational Medicinal Product
IIT	Investigator-initiated Trial
ISO	International Organisation for Standardisation
ITT	Intention to treat
KlinV	Verordnung über klinische Versuche in der Humanforschung (in English: ClinO, in French OClin)
LPTth	Loi sur les produits thérapeutiques
LRH	Loi fédérale relative à la recherche sur l'être humain
MD	Medical Device
MUSHRA	Multi-Stimulus Test with Hidden Reference and Anchor
N/A	Not Applicable
OClin	Ordonnance sur les essais cliniques dans le cadre de la recherche sur l'être humain (in German : KlinV, in English : ClinO)

OLSA	Oldenburger Satztest
PI	Principal Investigator
PL	Project Leader
PM	Product Manager
PPT	Phoneme Perception Test
REM	Real-Ear Measurement
RIC	Receiver-In-The-Channel device
SDV	Source Data Verification
SNR	Signal-to-Noise Ratio
SOP	Standard Operating Procedure
SPC	Summary of product characteristics
SPL	Sound Pressure Level
SRT	Speech Reception Threshold
SUSAR	Suspected Unexpected Serious Adverse Reaction
TEN test	Threshold-Equalizing-Noise test
TMF	Trial Master File
UAT	User Acceptance Test
UCL	UnComfortable Level
WaKo	Einsilber-Reimtest nach von Wallenberg und Kollmeier

STUDY SCHEDULE

(AGEK 4.2; SPIRIT #13; ICH E6 6.4.2)

Studies are organized in, a potential pre-study if needed, and the main study itself. A pre-study would be organized as follows:

Study Period	Screening	Pre-study appointments		Follow-up (final appointment)
Visit Number	1	2	3	4
Time [hrs]	1.5	2	2	2
Audiological History	x			
Physical Examination of Ear and Ear Canal	x	x	x	x
Audiogram	x			x
Tinnitus Matching	x			x
Check In- /Exclusion Criteria	x			
Decision Subject Participation	x			
Subject Information and Informed Consent	x			
Encoded Subject ID	x			
eCRF Screening	x			
eCRF Audiometry	x			x
Randomisation	x			
Hearing System Fitting	x	x	x	
Objective and Subjective Measurements		x	x	(x)
eCRF Objective and Subjective Measurements		x	x	(x)
Introduction to Handling		x	x	
Scheduling Next Visit		x	x	
eCRF Final Appointment				x
Capture of Adverse Events and Device Deficiencies	x	x	x	x

Table 1a: Pre-study: N = max 5

Study Period	Screening	Study appointments										Final Appointment
		2	3	4	5	6	7	8	9	10	11	
Visit Number	1	2	3	4	5	6	7	8	9	10	11	12
Time [hrs]	1.5	2	2	2	2	2	2	2	2	2	2	2
Audiological History	x											
Physical Examination of Ear and Ear Canal	x	x	x	x	x	x	x	x	x	x	x	
Audiogram	x											x
Tinnitus Matching	x											x
Check In- /Exclusion Criteria	x											
Decision Subject Participation	x											
Subject Information and Informed Consent	x											
Encoded Subject ID	x											
eCRF Screening	x											
eCRF Audiometry	x											x
Randomisation	x											
Hearing System Fitting	x											
Objective and Subjective Measurements		x	x	x	x	x	x	x	x	x	x	(x)
eCRF Objective and Subjective Measurements		x	x	x	x	x	x	x	x	x	x	(x)
Introduction to Handling		x	x	x	x	x	x	x	x	x	x	
Scheduling Next Visit	x	x	x	x	x	x	x	x	x	x	x	
eCRF Final Appointment												x
Capture of Adverse Events and Device Deficiencies	x	x	x	x	x	x	x	x	x	x	x	x

Table 1b: Main study: N = max 30 (no pre-study subjects)

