6.1 General study design and justification of design

(ICH/E6 6.4.2, 6.4.5; AGEK 4.2; SPIRIT #8)

ICH: The scientific integrity of the trial and the credibility of the data from the trial depend substantially on the trial design.

ICH: A description of the type/design of trial to be conducted (e.g., double-blind, placebo-controlled, parallel design) and a schematic diagram of trial design, procedures and stages.

ICH: The expected duration of subject participation, and a description of the sequence and duration of all trial periods, including follow-up, if any.

A methodical evaluation of new CE-Labelled Phonak Hearing Systems is intended to be conducted on hard of hearing participants to grant quality control prior to product launch in spring or in fall per year. The aim of the investigation is to continuously ensure zero-defect overall performance of the new hearing systems as well as maximum benefit for the participant with the devices in comparison to previously outstanding Phonak Hearing Systems and to equivalent strong competitor devices across 10 years (October 2015 to 2025). This will be a controlled, single blinded (participants), randomised (testing method), cross-over (investigational product) active comparator study which will be conducted mono centric at Sonova AG Headquarters based in Stäfa.

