6.2.1 Randomisation

Randomization and concealment of randomization list is generated by the Principle Investigator using a script written in the program MatLab. The randomization is applied to all investigational products for both the lab trials and the home trials. Furthermore, the order of the test method used per visit is liable to a randomization.

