11.2 Determination of Sample Size

ICH: The number of subjects planned to be enrolled. In multicentre trials, the numbers of enrolled subjects projected for each trial site should be specified. Reason for choice of sample size, including reflections on (or calculations of) the power of the trial and clinical justification.

Based on numerous publications in the field of audiology research using standardized measurement methods testing hearing impaired subjects as well as on Sonova AG's extensive study experience, a number of maximum 20 subjects per study is sufficient to obtain statistically significant results on a significance level of 5%.

In the case of the pre-study a maximum of 5 subjects is included, since merely the study concept needs to be proved, and no inferential but only descriptive statistics is carried out. Later, during the main study, both descriptive and inferential statistics are executed. In the past, typically 20 subjects participated per study leading to significant results approaching the primary objective (zero-defect overall performance of the new Phonak Hearing Systems). To tackle the secondary objective (product benchmark) a number up to 30 subjects have taken part in several previous investigations. This case is founded in the fact that a study design of parallel groups, either containing 10 or 15 subjects each, is applied as soon as more than one competitor device is compared to the Phonak Hearing System. For this reason, an appropriate number of subjects will be included during the planned investigations.

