11.4.1 Datasets to be analysed, analysis populations

ICH: The selection of subjects to be included in the analyses (e.g., all randomized subjects, all dosed subjects, all eligible subjects, evaluable subjects).

The data of all participants and measurement methods will be analysed. Subgroups typically composed are hearing loss dependent groups (mild, moderate, severe, profound) and groups depending on their experience level wearing hearing instruments or using accessories (non-experienced, short-term, experienced, long-term user). In case of a subject withdrawal, only complete data sets of a measurement method will be used as part of the statistical analysis.

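### Parallel benchmark groups of 10 or 15 have neither a balancing step nor an adjusted test specified for hearing loss and hearing-aid experience

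*Combined protocol and SAP*

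**What the plan says.** - **Design.** The synopsis allows "Active comparator study, controlled, single blinded, randomised, cross-over or parallel design". Section 6.1 instead describes a "randomised (testing method), cross-over (investigational product) active comparator study". Section 11.2 says that "a study design of parallel groups, either containing 10 or 15 subjects each, is applied" once a second competitor enters the comparison. The maximum per main study is 30.
- **Population.** The synopsis and section 7.1 admit "Adult hearing impaired persons (minimum age: 18 years) with and without (experience with) hearing aids". Neither sets a hearing-loss range. Section 6.1 recruits losses suited to the form factor under test.
- **Relevance of the factors.** Section 3.8 says that sound processing in the inner ear depends on the degree of loss. Section 11.4.1 names hearing loss and experience as the usual subgroups.
- **Timing.** Table 1b places audiological history, audiogram and randomisation all at visit 1.
- **Allocation.** Section 6.2.1 states that "Randomization and concealment of randomization list is generated by the Principle Investigator using a script written in the program MatLab". Section 7.3 leaves assignment to chance among the first eligible volunteers. Neither section, nor the list of bias measures in 6.2, mentions stratification, blocking or minimisation.
- **Analysis.** Section 11.4 lists the t-test, Mann-Whitney, Wilcoxon and correlation coefficients at a 5% level, with no covariate. Section 11.4.3 applies the same approach to the benchmark.

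**The concern.** Where each person tests one device, the device contrast is a contrast between different people. With 10 or 15 per group, chance can put noticeably more new users, or more severe losses, on one device. An unadjusted test cannot separate that from a device effect, although both factors are known before the first device measurement. Section 13 lets results support product claims, so a single benchmark may be read on its own. A visible imbalance is then hard to answer after the fact.

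**Working it through.** The documents give no effect size, SD or power for the benchmark, so there is no planned figure to reproduce.

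**Inputs.** Groups of 10 or 15 and the maximum of 30 come from the protocol. Three inputs are assumptions, because the documents give no figures: a factor present in half the participants; its effect g in within-group SD; and the share R² of outcome variance that the factors explain.

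**1. How often imbalance arises** (hypergeometric, total fixed)
- 10 v 10, 10 of 20 experienced: P(X≤3) + P(X≥7) = 0.179.
- 15 v 15, 15 of 30 experienced: P(X≤5) + P(X≥10) = 0.143.
- Three groups of 10, 15 of 30 experienced: largest minus smallest count is 4 or more in 26% (100,000 permutations). A given pair differs by 4 or more in 12%.
- 10 v 10 with a 30% or 20% minority: a difference of 4 or more in 14% or 9%.

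**2. What it does to the contrast**
- Residual SE of a difference = √(2/n): 0.447 SD at 10 per group, 0.365 SD at 15.
- A 7:3 split with g = 1 shifts the contrast by 1 × (0.7 − 0.3) = 0.4 SD.
- The unadjusted test's SE also carries the factor's variance: √(1 + 0.25) × 0.447 = 0.50 SD. The shift is 0.4/0.50 = 0.8 of that SE.
- With g = 0.5 the shift is 0.2 SD, under half an SE.
- A shift of a full residual SE with g = 1 needs 8:2 or worse at 10 v 10 (2.3%) or 11:4 or worse at 15 v 15 (2.7%).

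**3. Type I error of the unadjusted t-test** (100,000 simulated trials per case)
- Over all allocations: 5.0% to 5.2%.
- At 10 per group, given an imbalance of at least 40 percentage points (18% of trials): 11% with g = 1, 20% with g = 2.

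**4. What adjustment gains and costs**
- The SE falls by 1 − √(1 − R²), before the cost of estimating the covariate terms: 5% at R² = 0.1, 11% at 0.2, 16% at 0.3.
- With q = 2 covariates, unbalanced allocation and N people, the expected variance relative to the unadjusted test is about (1 − R²) × [1 + q/(N − q − 3)].
- N = 20: the factor is 1 + 2/15 = 1.133, so break-even is R² = 1 − 15/17 = 12%.
- N = 30: the factor is 1 + 2/25 = 1.08, so break-even is R² = 1 − 25/27 = 7%.
- Simulated power at 10 per group, for a device difference of about 1.2 SD: 72% to 75% at R² = 0.2; 72% to 81% at R² = 0.3; 73% to 67% if the factors explain nothing.

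**The case against.** **A full-SE shift is not frequent.** A reader might infer that imbalance often moves the result by a whole standard error. The documents give no effect for either factor, and with a 1 SD factor a full-SE shift is rare (step 2). It becomes frequent only with a factor of about 1.5 SD or more. This objection stands.

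**Validity is intact.** A reader might infer an inflated false-positive rate. Over all allocations there is none, because the ordinary SE already includes chance imbalance. This stands too. The conditional rates in step 3 describe credibility in one unbalanced study.

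**The parallel contrast may be within person.** More than one competitor plus the Phonak device makes at least three devices. Two groups of 15, or of 10, cannot hold three devices at one per person; within the maximum of 30, only three groups of 10 can. Sections 6.1 and 11.2 therefore leave open that each group compares Phonak with one competitor within person. If so, imbalance does not bias the main benchmark contrast, and only comparisons between competitors are between people. The text does not settle this, so the objection narrows the point without removing it.

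**Silence is not a statement, and the mix may be narrow.** Section 6.2.1 does not say what the script does, so it does not establish that allocation ignores these factors. Matching loss to form factor may also narrow the spread of hearing loss, but it does nothing for experience.

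**It is a secondary aim.** Section 11.1 disclaims a specific hypothesis. Even so, section 11.4 plans 5% tests, and subgroup summaries by hearing loss or experience do not adjust the device comparison.

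**Conclusion.** The point holds as a gap in specification. For any between-person device comparison, the plan names no balancing and no adjustment for two baseline factors that it treats as important. Sizeable imbalance is common: 18% at 10 v 10 and 14% at 15 v 15 for a 50:50 factor, and less often for a rarer one at 10 v 10. The loss is precision, about 11% to 16% of the SE before the cost of estimation if the factors explain 20% to 30% of variance, together with the standing of any one unbalanced result. The 50:50 split and the explained variance are assumptions. The point does not apply to cross-over studies or to within-person contrasts.

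**What to change.** **In 11.4**, for any between-person device comparison, replace the unadjusted t or Mann-Whitney test with a linear model for device that includes the visit-1 pure-tone average and hearing-aid experience (none versus any). Use a rank-based analogue for ordinal or clearly non-normal outcomes. Fix the pure-tone average definition and the covariates before data are seen, and do not choose them after inspecting the imbalance. If a study recruits only one experience group, that term drops out.

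**Across the synopsis, 6.1 and 11.2**, reconcile the design: state whether each person in a parallel group tests one device or Phonak plus one competitor, and which contrasts are within person.

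**In 6.2.1**, state whether allocation uses either factor. Balancing, for example by minimisation, is optional. Four-stratum permuted blocks are too sparse: 20 to 30 people over four strata is 5 to 7.5 each, and the very small blocks needed would be predictable to investigators, who mount the devices themselves.

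**Cost.** No extra people, visits or measurements. The model uses two degrees of freedom and loses power if the factors explain less than roughly 10% of variance: about 6 percentage points at 10 per group in the worst case, where they explain nothing.

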1. STUDY ADMINISTRATIVE STRUCTURE

(ICH/E6 6.1.2-6.1.7; AGEK 1.1; SPIRIT 5a-d)

This section contains complete contact details.

1.3 Statistician ("Biostatistician")

(ICH/E6 6.1.7; SPIRIT 5a-d)

ICH: Name(s) and address(es) of the clinical laboratory(ies) and other medical and/or technical department(s) and/or institutions involved in the trial.

The role as the Statistician is adopted by the Principle Investigator.

